9.0 Confidentiality, Privacy and Data Management

Please see HRP-598 - Research Data Plan Review Form

10.0 Data and Safety Monitoring Plan

N/A: This study does not involve more than minimal risk to subjects, and the magnitude of harm/discomfort is not greater than that ordinarily encountered in daily life.

11.0 Risks

Risk involved in participating in this study are low aside from identification of a suicidal student, in which case measures are already currently in place in each school building to address.

12.0 Potential Benefits to Subjects and Others

12.1 Potential Benefits to Subjects

Potential benefit to subjects of positive screenings include a referral to SAP to receive support in managing their MDD.

12.2 Potential Benefits to Others

The potential public health impact of the proposed project cannot be overstated. MDD is a prevalent, disabling and a growing US public health problem. The problem is identified by national organizations focused on our country's health care priorities (Healthy People 2020, US Department of Health and Human Services). MDD leads both to functional impairment and higher rates of morbidity and mortality. In addition, MDD leads to significant social and economic consequences, including increased use of health resources and lost work productivity. A public health goal should include identification of those at risk for depression with the delivery of interventions to these individuals. Schools are a point of intervention with a high potential for early identification and prevention. Currently, fewer than 2 out of every 100 adolescents receives guideline-concordant major depression screening. We propose reaching nearly 80 of every 100 adolescents in the school setting, vastly increasing the identification of adolescents suffering from MDD with a goal to decrease both morbidity and mortality. Schools are an ideal partner for this approach, given their tremendous reach across the nation to nearly all adolescents.

13.0 Sharing Results with Subjects

Individual results will not be shared with other participants.

14.0 Subject Stipend (Compensation) and/or Travel Reimbursements

N/A

15.0 Economic Burden to Subjects

15.1 Costs

There are no financial costs associated with participating in this research.

15.2 Compensation for research-related injury

N/A

16.0 Resources Available

16.1 Facilities and locations

Screening will take place in each of the 8 school buildings previously identified.

16.2 Feasibility of recruiting the required number of subjects

All 8 school districts have already expressed interest in participating as evidenced through letters of support obtained during the proposal process. Current relationships through past and present programming with the school districts created feasibility for recruitment.

16.3 PI Time devoted to conducting the research

██████████ will monitor the progress of the study during all phases and hold bi-weekly meetings with research staff.

16.4 Availability of medical or psychological resources

It is not anticipated that medical or psychological resources will be needed on site, given that study procedures are minimal risk. However, students with suicidal intent will receive immediate evaluation and referral to emergency care as per current school protocols. PA schools are required to have a plan to address suicidal students. A QPR trained staff member will be available at the time of screening. Students with a PHQ-9 score ≥ 11 will proceed to Student Assistance Program triage as per the standard of care by which students exhibiting concerning behavior (outbursts, declining grades) would be referred for assessment.

16.5 Process for informing Study Team

The investigators and project coordinator/study staff have completed their required Collaborative IRB Training Initiative (CITI) in the protection of human research subjects. The study team will be educated on the importance of confidentiality, and proper data handling and storage. Four study team members will also complete the Question, Persuade, Refer suicide triage training in order to assist the school staff as needed during the time of actual screening.

17.0 Other Approvals

17.1 Other Approvals from External Entities

N/A

17.2 Internal PSU Committee Approvals

Check all that apply:

- Anatomic Pathology – Hershey only – Research involves the collection of tissues or use of pathologic specimens. Upload a copy of HRP-902 - Human Tissue For Research Form on the “Supporting Documents” page in CATS IRB. This form is available in the CATS IRB Library.
- Animal Care and Use – All campuses – Human research involves animals and humans or the use of human tissues in animals
- Biosafety – All campuses – Research involves biohazardous materials (human biological specimens in a PSU research lab, biological toxins, carcinogens, infectious agents, recombinant viruses or DNA or gene therapy).

- Clinical Laboratories – Hershey only – Collection, processing and/or storage of extra tubes of body fluid specimens for research purposes by the Clinical Laboratories; and/or use of body fluids that had been collected for clinical purposes, but are no longer needed for clinical use. Upload a copy of HRP-901 - Human Body Fluids for Research Form on the “Supporting Documents” page in CATS IRB. This form is available in the CATS IRB Library.
- Clinical Research Center (CRC) Advisory Committee – All campuses – Research involves the use of CRC services in any way.
- Conflict of Interest Review – All campuses – Research has one or more of study team members indicated as having a financial interest.
- Radiation Safety – Hershey only – Research involves research-related radiation procedures. All research involving radiation procedures (standard of care and/or research-related) must upload a copy of HRP-903 - Radiation Review Form on the “Supporting Documents” page in CATS IRB. This form is available in the CATS IRB Library.
- IND/IDE Audit – All campuses – Research in which the PSU researcher holds the IND or IDE or intends to hold the IND or IDE.
- Scientific Review – Hershey only – All investigator-written research studies requiring review by the convened IRB must provide documentation of scientific review with the IRB submission. The scientific review requirement may be fulfilled by one of the following: (1) external peer-review process; (2) department/institute scientific review committee; or (3) scientific review by the Clinical Research Center Advisory committee. NOTE: Review by the Penn State Hershey Cancer Institute Scientific Review Committee is required if the study involves cancer prevention studies or cancer patients, records and/or tissues. For more information about this requirement see the IRB website at: <http://www.pennstatehershey.org/web/irb/home/resources/investigator>

18.0 Multi-Site Research

N/A

19.0 Adverse Event Reporting

19.1 Reporting Adverse Reactions and Unanticipated Problems to the Responsible IRB

In accordance with applicable policies of The Pennsylvania State University Institutional Review Board (IRB), the investigator will report, to the IRB, any observed or reported harm (adverse event) experienced by a subject or other individual, which in the opinion of the investigator is determined to be (1) unexpected; and (2) probably related to the research procedures. Harms (adverse events) will be submitted to the IRB in accordance with the IRB policies and procedures.

20.0 Study Monitoring, Auditing and Inspecting

20.1 Auditing and Inspecting

The investigator will permit study-related monitoring, audits, and inspections by the Penn State quality assurance program office(s), IRB, the sponsor, and government regulatory bodies, of all study related

documents (e.g., source documents, regulatory documents, data collection instruments, study data etc.). The investigator will ensure the capability for inspections of applicable study-related facilities (e.g., pharmacy, diagnostic laboratory, etc.).

21.0 Future Undetermined Research: Data and Specimen Banking

N/A

21.1 Data and/or specimens being stored

N/A

21.2 Location of storage

N/A

21.3 Duration of storage

N/A

21.4 Access to data and/or specimens

N/A

21.5 Procedures to release data or specimens

N/A

21.6 Process for returning results

N/A

1.0 Objectives

1.1 Study Objectives

OBJECTIVE 1. Partnering with 14 PA public high schools (letters of commitment obtained for all 14 high schools) serving an estimated 12,582 predominantly minority, rural, urban, and/or low socioeconomic status (SES) students, we will conduct a randomized controlled trial, with student randomization by grade, to compare the effectiveness of universal school-based screening for adolescent major depressive disorder (MDD) versus the existing process of targeted screening based on concerning behavior.

- *Hypothesis 1: Universal screening will increase the number of adolescents with MDD screened, identified and engaged in treatment (MDD composite).*
- *Hypothesis 2 (Moderating): Universal screening will increase the historically poorer rates of MDD screening, identification and treatment engagement for females*
- *Hypothesis 3 (Moderating): Universal screening will increase the historically poorer rates of MDD screening, identification and treatment engagement for rural adolescents*

OBJECTIVE 2. Analyze the impact of MDD screening on secondary outcomes currently collected by the school's Student Assistance Program (SAP) and the school district. These data will be obtained in aggregate by grade level at each participating school (a total of 64 data points for each item; 4 grades x 14 schools, see note below re: PCORI). Please note, secondary outcomes may no longer be available due to COVID-19 school closures and cancellation of state standardized testing.

- *Hypothesis 1. Standardized test scores (e.g. Keystone exams, PSAT, SAT, ACT) will improve in school populations with universal MDD screening secondary to earlier identification, treatment referral and engagement.*
- *Hypothesis 2. Student school policy violations and suspensions will remain unchanged among school populations with the universal MDD screening approach.*

Please note: We recently received funding from the Patient Centered Outcomes Research Institute (PCORI) for a complementary project to the one above. Aims for this HRSA study and the PCORI study have been adjusted with the permission of both organizations to be complementary but distinct. The PCORI project is in contract negotiations but will involve only urban school districts focusing on the effectiveness of MDD screening in minority populations (deleted objective #1, hypothesis #2 above) HRSA will remain focused on rural schools, which are primarily white (hence the rationale for removing objective #1, hypothesis #2). Secondary outcomes have similarly been adjusted to be complementary but distinct from each other. The study will be registered as one RCT in clinicaltrials.gov again with the approval of the funding organizations. The final analysis will involve both the HRSA and PCORI funded schools.

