Despite the rising rates of depression, there has been no change in mental health treatment among adolescents with a MDD episode from 2005-2014.⁶ Only 36-44% of children and adolescents with MDD receive treatment, underscoring that MDD is underdiagnosed and undertreated.⁶ This disparity is especially pronounced for disadvantaged populations. Even for those who have a primary care provider, data from HealthyPeople.gov indicates a steady decline in rates of screening with only 1.4% of primary care office visits including MDD screening as of 2009- 2011.⁴ In addition to minorities, rural youth and those of lower SES receive fewer preventive care services than their white, urban, high SES counterparts, further limiting their access to MDD screening in the context of well-care.^{20,21}

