8.2 Sample size determination

A total of 4,820 (estimated) students in each randomized group (an overall sample size of 9,640 [estimated]) yields >99% statistical power to detect a difference of 3% versus 6% using a 2-sided test conducted at a Type I error rate of 5% in a mixed effect logistic regression model.

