8.3 Statistical methods

The principles of intention-to-treat (ITT) will be used for all statistical analyses related to primary and secondary aims. For the primary aim comparing universal to targeted screening, the statistical analysis will be conducted using a mixed effects logistic regression model. The primary outcome, MDD composite, will be an indicator whether a student was screen positive (or concerns raised in the targeted screening arm), identified as having MDD and subsequently engaged in treatment (1=yes, 0=no). The model will include a fixed effect for randomized group (0=targeted screening, 1=universal screening) and a random effect for school. The random effect accounts for correlation among students enrolled within the same school. The primary parameter of interest will be the log odds of MDD composite in the universal screening group compared to the targeted screening group. Statistical significance of the log odds will be assessed using a 2-sided Wald test. Point estimates for the odds ratio along with a 95% confidence interval will be reported.

For the analysis of Hypotheses 2 and 3 (Objective 1) evaluating universal screening and targeted screening by selected subgroups, the same mixed effects logistic regression modeling framework will be used, but the model will be extended by including a fixed effect for subgroup and an interaction effect for subgroup by randomized group. The interaction term will be the parameter of interest. A significant interaction term indicates that rates of MDD treatment engagement for universal versus targeted screening differ by subgroup level (e.g. female vs. male). For the secondary analyses (Objective 2) that evaluates universal screening and targeted screening based on school SAP data, we will have only 64 total data points (4 grades in each of the 14 schools). Mixed-effects linear (continuous outcomes) and logistic regression (binary outcomes) will be used, as appropriate, with a fixed effect for randomized group and a random effect for school. The parameter of interest will be the log odds for the universal compared to the targeted screening group. Due to the smaller sample size used for these outcomes, these analyses will be considered to be primarily hypothesis-generating. Potential mediating variables (socioeconomic status, ratio of guidance counselors to students and availability of school-based mental health services) will be evaluated for both the Objective 1 and 2 hypotheses.

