Additional secondary outcomes will include MDD screen results, MDD concern prompting Student Assistance Program triage, MDD identification and MDD treatment engagement analyzed individually (rather than as part of MDD composite). Finally any suicidal adolescents (suicidal thoughts [positive response to PHQ-9 item 9], attempts and completed) will be analyzed as a secondary outcome.

We need to collect data for individuals for 3 main reasons. First, we expect approximately 20% of students to opt out from the study, with opt out rates varying by grade. Aggregate data would necessarily include outcomes for students who are not enrolled in the study. This is particularly problematic for the universal screening group because students who opt out will not be offered the depression screening tool (PHQ-9). Second, we need to obtain gender and race/ethnicity to conduct important planned secondary analyses (subgroup analyses) that will examine efficacy of universal screening by these groups. In particular, we expect that females and minority students will have much higher rates of major depression disorder identified in the universal screening group. Third, in the

universal screening group, we will be able to link responses to the PHQ-9 to outcomes, which will allow for estimation of important measures such as the false positive rate of the PHQ-9 (score ≥ 11 , but SAP process determines no further referrals are needed). These measures will inform decision-making regarding the potential for implementation of the intervention (in other schools) should the results of the trial ultimately show efficacy.

Efforts will be made to ensure completeness of data where possible, but missing data will occur for a number of anticipated reasons. First, a student may move during the course of the school year to another school district or drop out from school entirely. No data will be collected after this time point. Second, parents may opt out their child from the study at any time during the school year. Third, students who turn 18 during the school may decide to opt out of the study themselves. In both of these instances, data from SAP referrals that occur after opting out will not be collected for purposes of the study. Fourth, during the one-time universal screening phase, students may decide to leave data forms incomplete, including the PHQ-9. To decrease these instances, the PHQ-9 will be taken on an iPad program and the survey will alert if the form is left incomplete.

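### The rural-by-arm test for Hypothesis 3 cannot separate rurality from race or ethnicity, because the pooled rural schools are mainly white and the urban districts come from a minority-focused project

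*Combined protocol and SAP*

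**What the plan says.** All references are to the current version of the protocol, the one that lists 14 schools.

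- **Hypothesis.** Section 1.1, Objective 1, Hypothesis 3 names rural status as a moderator of the screening effect.
- **Schools.** The funding note in section 1.1 says of the HRSA part that "HRSA will remain focused on rural schools, which are primarily white". It says that the PCORI project "will involve only urban school districts focusing on the effectiveness of MDD screening in minority populations". The same note puts both sets of schools into one final analysis.
- **Model.** For Hypotheses 2 and 3, section 8.3 takes the primary mixed logistic model and says that "the model will be extended by including a fixed effect for subgroup and an interaction effect for subgroup by randomized group". The interaction is the parameter of interest. Race and ethnicity do not appear in the rural model. The variables to be examined as mediators are socioeconomic status, counselor ratio and school mental health services.
- **Race and ethnicity.** Section 1.3 collects both for each student. Section 8.3 says that subgroup analyses by gender and race/ethnicity are planned, and adds that "we expect that females and minority students will have much higher rates of major depression disorder identified in the universal screening group". No model in the plan holds race or ethnicity together with rural status.

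**The concern.** Arms are assigned by grade within schools, so the arms are comparable inside each school. That does not make rural students comparable with urban students. A rural-by-arm term compares two screening effects across two groups of districts that, by the protocol's own description, differ in racial make-up.

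If the screening odds ratio differs between minority and white students, that difference enters the rural-by-arm term. The random school effect does not remove it: it is an intercept and absorbs differences in baseline rate, not in the effect of screening. Testing race and rurality one at a time does not help either, because each one-factor interaction then carries part of the other.

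At stake is the reading of a named hypothesis. If minority students have the larger odds ratio, the planned term is pushed below 1. A real rural advantage could then be missed, or a difference due to race mix could be reported as screening working less well for rural adolescents.

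**Working it through.** **1. The plan's own figure.** Sections 8.1 and 8.2 give enrolment of 3,900 rural and 8,150 urban students, 20% opt-out, and rates of 3% versus 6%. (3,900 + 8,150) × 0.8 = 9,640, or 4,820 per arm, as stated. For the main effect:

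- log OR = ln[(0.06/0.94)/(0.03/0.97)] = 0.7246
- SE = √[1/(4,820 × 0.03 × 0.97) + 1/(4,820 × 0.06 × 0.94)] = 0.1040
- z = 6.97, so power exceeds 99%, as stated.

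This is power for the primary comparison. The documents give no figure for Hypothesis 3.

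**2. Inputs for the rural-by-arm term.**

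- From the documents: rural students per arm 3,900 × 0.8 / 2 = 1,560; urban 8,150 × 0.8 / 2 = 3,260; control rate 3%; two-sided 5% test.
- Assumed, because the documents are silent: minority share 5-15% in rural and 50-80% in urban schools; OR 1.8 in white students; minority OR larger by a factor R of 1.25 or 1.5; no true rural effect; equal control rates; no variation in the screening effect between schools.

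**3. One case in full (10% rural, 70% urban, R = 1.5).**

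- White students, universal arm: odds 0.03/0.97 × 1.8 = 0.0557, rate 5.273%.
- Minority students, universal arm: odds 0.03/0.97 × 2.7 = 0.0835, rate 7.707%.
- Rural rate: 0.10 × 7.707 + 0.90 × 5.273 = 5.52%, OR against 3% = 1.888.
- Urban rate: 0.70 × 7.707 + 0.30 × 5.273 = 6.98%, OR = 2.425.
- Rural:urban ratio of odds ratios = 1.888 / 2.425 = 0.78, although rurality has no effect.
- SE of its log, from the sum of 1/(n p(1−p)) over the four cells, = 0.223. z = ln(0.7785)/0.2227 = −1.12, so a nominal 5% test rejects about 20% of the time.

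**4. The range.**

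| Minority share, rural / urban | R = 1.25: ratio (rejection) | R = 1.5: ratio (rejection) |
|---|---|---|
| 15% / 50% | 0.92 (6%) | 0.86 (10%) |
| 10% / 60% | 0.89 (8%) | 0.81 (16%) |
| 10% / 70% | 0.87 (9%) | 0.78 (20%) |
| 5% / 80% | 0.84 (12%) | 0.73 (29%) |

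**5. When nothing happens.** With R = 1 the ratio is 1.00. If minority students have control odds 1.5 to 3 times higher but the same OR of 2.06 (3% to 6%), the ratio at 10%/70% is also 1.00 to two decimals. A difference in baseline rate alone does not cause the problem.

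**6. Variation between schools.** Rural status belongs to the district, so variation in the screening effect between schools widens the interval. With an assumed SD of 0.3 on the log-odds scale, 9 rural schools (section 8.1) and 14 − 9 = 5 urban schools, SE = √[0.2227² + 0.3² × (1/9 + 1/5)] = 0.279. The 20% in step 3 falls to about 15%. The rejection rates in step 4 are therefore approximate.

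**7. Does a joint model repair it?** Logistic models were fitted to expected cell counts (10%/70%, R = 1.5, white OR 2.06, no school effect). The rural-by-arm ratio is 0.779 in the planned model, 0.778 with a race main effect added, and 1.000 with race-by-arm added as well. The SE rises from 0.218 to 0.265, a variance ratio of 1.47. Over minority shares of 5-20% rural and 50-90% urban, the variance ratio runs from 1.09 to 3.1, depending on overlap.

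**The case against.** The strongest reply is that the planned contrast answers a legitimate question. Section 1.3 defines rural by district, and section 8.3 reads a significant interaction only as a difference between subgroup levels. Nothing in the plan claims an effect of rurality net of race. This stands: as a description of rural against urban districts the planned model is sound, and it should stay.

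Second, the expectation about minority students concerns rates of identification in one arm. It is not a statement about odds ratios for the composite, and the same sentence covers females, whose higher rates section 2.3 presents as higher prevalence. This also stands in part. The sentence follows directly on efficacy by subgroup, so it can be read as expecting a larger effect, but it does not have to be.

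Third, the distortion works against Hypothesis 3. At R = 1.5 the chance of false support for it is 0.04-0.4%, below the nominal 2.5%. The risk is a missed or reversed moderator, not a false claim in its favour.

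Three stronger readings are tempting, and the documents do not support them.

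- A reader might take the remark in section 2.3 that "rural youth and those of lower SES receive fewer preventive care services than their white, urban, high SES counterparts" as setting rural youth against one joint comparator that is not enrolled here. The sentence opens by naming minorities as well, so three parallel contrasts (race, rurality, SES) are the natural reading.
- A reader might infer that the urban schools were selected for their minority students. Section 1.1 describes the focus of the project and gives neither a selection rule nor percentages.
- A reader might see dropping the minority hypothesis as inconsistent, since urban schools supply 8,150 of 12,050 students (68%). Section 1.1 explains it as a division of aims between two funders.

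**Conclusion.** The point holds as a limit on interpretation. The planned rural-by-arm term cannot tell rurality from race or ethnicity in this set of schools, and nothing else in the plan can. If the screening OR is larger in minority students, the term is biased below 1. Under the assumptions above, this is modest at R = 1.25 (0.84-0.92, rejection 6-12%) and material at R = 1.5 (0.73-0.86, rejection 10-29%). If the OR does not differ by race, there is essentially nothing to correct. The documents do not say which case applies.

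A reader might go further and conclude that the Hypothesis 3 analysis is invalid, or that only a race-adjusted term may support a statement about rural students. Neither follows. The district contrast is valid as description. Adjustment for race and ethnicity would not isolate rurality either, since SES, counselor ratio and mental health services may still differ between districts. The primary comparison is unaffected.

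**What to change.** In section 8.3, under Hypothesis 3:

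1. Keep the planned rural-by-arm model and label it as the descriptive contrast between rural and urban districts.
2. Prespecify a supporting model that adds main effects of race and ethnicity and their interactions with arm. A main effect alone is not enough (step 7 of the working).
3. Report both rural-by-arm estimates with 95% confidence intervals, and tabulate race and ethnicity by rural status so that the overlap is visible.
4. State that a rural-urban difference will not be attributed to rurality itself unless it persists in the joint model, and that other district differences remain even then.

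No new data are needed, because race and ethnicity are already collected per student. The cost is precision: the variance of the adjusted term rises about 1.5-fold in the worked case, and up to about 3-fold if few minority students attend rural schools and few white students attend urban ones. The supporting model may then be inconclusive, and the report should say so.
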